631 Site personnel will call all subjects at 1 week (7 to 13 days) to encourage compliance with treatment

and to confirm that there are no technical problems playing the binocular game for those assigned to

633 binocular treatment. Site personnel will call subjects in the continued spectacle treatment group

634 who switch to binocular treatment at 9 weeks (7 to 13 days after the 8-week visit), again to

635 encourage compliance with treatment and to confirm that there are no technical problems playing

636 the binocular game for those assigned to binocular treatment.

637 **3.5 Follow-up Visit Schedule**

638 The follow-up schedule is timed from randomization as follows:

- 639
 1-week phone call (7 to 13 days from randomization) to inquire about issues with the
 640
 641
 641
 641
 641
- 641 be completed by site personnel)
- 4 weeks ± 1 week (primary outcome)

- 643 8 weeks ± 1 week (secondary outcome)
- Binocular final visit
 - Spectacle group switched to binocular treatment and followed for 8 weeks
- 9-week phone call (Spectacle group only: 7 to 13 days from 8-week exam) to inquire about
 issues with the binocular game (if applicable) and to encourage compliance with treatment
 for all groups (to be completed by site personnel)
- 649
 16 weeks ± 1 week (final visit for group originally randomized to continued spectacle treatment who were switched to binocular treatment)
- 651

652 Additional non-study visits can be performed at the discretion of the investigator.

653 **3.6 Resolution of Amblyopia**

Subjects achieving amblyopic-eye VA equal to or better (0 lines or more lines better) than the better
of the fellow-eye VA at baseline or 4-week visit, will be considered to have resolved and may
discontinue binocular treatment, although these subjects will still return for all remaining follow-up
exams.

658 3.7 Optional Post 8-week Treatment

659 For children originally randomized to binocular treatment, the study ends at 8 weeks.

660

661 Children who were originally assigned to continued spectacle treatment will be offered binocular

treatment for 8 weeks following the 8-week visit. The study will end at the 8-week exam for

663 children who choose not to receive binocular treatment. Children receiving binocular treatment at

the 8 week exam will return at 16 weeks for a follow-up visit. The study will end for these children

at the 16-week visit.

666 **3.8 Follow-up Visit Testing Procedures**

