667 Subjects will be seen at follow-up visits as outlined in *section 3.5*. A Masked Examiner must

668 complete distance VA and stereoacuity testing at these visits (*section 3.8.1*). All procedures will be

669 performed with the subject's current spectacle correction. If a subject currently wears spectacles

but is not wearing them at the follow-up examination for whatever reason, testing must be

- 671 performed in trial frames.
- 672

673 Prior to the Masked Examiner entering the room, subjects and parents should be instructed not to 674 discuss their treatment with the Masked Examiner.

675

676 The following study procedures are performed at each visit:

677 678

- 1. ATS Diplopia Questionnaire
- The child and parent(s) will be specifically questioned regarding the presence and frequency of any diplopia within the last 2 weeks using a standardized diplopia assessment (*see ATS Miscellaneous Testing Procedures Manual*). The diplopia assessment must be performed prior to any other testing during the exam.

684		
685	2.	Symptom Survey
686		• The child and parent(s) will complete a 5-item symptom survey regarding the
687		presence of various ocular symptoms within the past 2 weeks (see ATS
688		Miscellaneous Testing Procedures Manual). The symptom survey must be
689		performed prior to any other testing during the exam.
690		
691	3.	Distance VA Testing (masked):
692		• Monocular distance VA testing will be performed in the current spectacle correction in
693		each eye using the same VA testing method that was used at enrollment, as described in
694		the ATS Testing Procedures Manual.
695		• The ATS HOTV testing protocol will always be used to test VA in the younger
696		age cohort (4 to <7 years at enrollment) whereas the E-ETDRS protocol will
697		always be used to test VA in the older cohort (7 to <13 years at enrollment).
698		 Testing must be completed without cycloplegia.
699		
700	4.	Stereoacuity Testing (masked):
701		• Near stereoacuity will be tested in habitual current refractive correction using the Randot
702		Butterfly test and Randot Preschool Stereoacuity test at near (1/3 meter).
703	_	
704	5.	Ocular Alignment Testing:
705		• Ocular alignment will be assessed in the current spectacle correction by the cover test,
706		simultaneous prism and cover test (SPCT) (if strabismus is present on cover testing), and
707		prism and alternate cover test (PACT) in primary gaze at distance (3 meters) and at near

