/08		(1/3 meter) as outlined in the ATS Procedures Manual.
709	3.	8.1 Masked Examiner
710	The M	asked Examiner must be certified to test VA and stereoacuity. Because the Masked
711	Exami	ner must be masked to the subject's treatment group, he/she must be someone other than the
712	manag	ing clinician (in many cases the managing clinician will be the investigator but this is not
713	require	ed).
714	3.9	16-Week visit
715	This v	isit is only for children randomized to continued spectacle treatment who opt to receive
716	binocu	lar treatment at the 8-week visit. At the 16-week visit, children will have the same testing as

described in *section 3.8*; however, testing does not need to be completed by a masked examiner.

718 Following this visit, the study will end for these children.

719 **3.10** Non-Study Visits and Treatment

- 720 Investigators may schedule additional visits at their own discretion. Subjects will continue to
- follow the study-specified follow-up schedule regardless of any non-study visits. No data will be
- 722 collected at non-study visits for the purpose of the study.
- 723

Investigators must not start any additional treatment (other than that outlined in *section 3.1*) prior tothe 8-week outcome visit.

727 CHAPTER 4: MISCELLANEOUS CONSIDERATIONS IN FOLLOW-UP

728 4.1 Contacts by the Jaeb Center for Health Research and Sites

729 The Jaeb Center serves as the PEDIG Coordinating Center. The Jaeb Center will be provided with

the parent's contact information. The Jaeb Center may contact the parents of the subjects.

- Permission for such contacts will be included in the Informed Consent Form. The principal purpose
- of the contacts will be to develop and maintain rapport with the subject and/or family and to help
- coordinate scheduling of the outcome examinations.
- 734

735 The site investigator or coordinator will contact the parents of each subject after the first week of

- the study to encourage compliance with treatment (spectacle or binocular) and to confirm that there
- are no technical problems playing the binocular game for those assigned to binocular treatment.

738 4.2 Subject Withdrawals

739 Parents may withdraw their child from the study at any time. This is expected to be a very

- 740 infrequent occurrence in view of the study design's similarity to routine clinical practice and short
- duration. If the parents indicate that they want to withdraw their child from the study, the

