- investigator personally should attempt to speak with them to determine the reason. If their interest
- is in transferring the child's care to another eye care provider, every effort should be made to
- comply with this and at the same time try to keep the child in the study under the new provider's
- 745 care.

746 4.3 Management of Refractive Error

747 Because of the short duration of the study and the requirement to have a cycloplegic refraction

- 748 within 7 months prior to enrollment, no cycloplegic refraction is mandated during the study.
- 749 Nevertheless, whenever the investigator suspects that refractive error may not be corrected
- according to study guidelines, a cycloplegic refraction should be performed. Change in spectacle
- correction is at investigator discretion, but must be prescribed according to the guidelines described
- in *section 2.2.1*. and spectacles will be paid for by the study.
- 753
- 754 Contact lenses are not allowed during the study.

755 4.4 Management of Strabismus

Because of the short duration of the study and the age group being studied, strabismus surgery is not
allowed prior to the end of the study. If surgery is performed, the date and type of surgery will be
recorded in the comment section of the Follow-up Examination Form.

759 **4.5 Risks**

760 **4.5.1 Development of Manifest Ocular Deviation or Diplopia**

- 761 Diplopia is expected to be rare based on our experience during the previous ATS18 study
- 762 comparing binocular treatment with patching. ²⁵
- 763
- 764 Data on frequency of diplopia will be collected from the child and parent(s) at each study visit.
- 765766 If treatment precipitates the development of a manifest ocular deviation (e.g., esotropia) and/or
- 767 diplopia, the parent will be advised to have the subject see the investigator as soon as possible. If a
- new manifest deviation is confirmed on examination, the decision as to whether to continue or
- 769 discontinue therapy will be left to the investigator's and parent's decision. If the investigator
- determines that binocular diplopia is present, continuation of treatment is also at the discretion of
- the investigator and parent(s). If amblyopia treatment is to be discontinued during the study, a

- 772 Protocol Chair should be called to discuss the case. Subjects discontinuing treatment during the
- 773 study will continue to be seen for the remaining regularly scheduled study visits.

774 4.5.2 Risks of Examination Procedures

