- 775 The procedures in this study are part of daily eye care practice in the United States and pose no 776 known risks. As part of a routine usual-care exam, the subject may receive cycloplegic/dilating eye
- 777 drops.

778 4.5.3 Delay in Use of Traditional Amblyopia Treatment

- 779 The subjects in the either treatment group will not be able to perform any patching, atropine,
- 780 Bangerter filter, or additional vision therapy treatment during the study.

781 4.6 **Reporting of Adverse Events**

782 No surgical procedures are part of the protocol. There are no expected long-term adverse events 783 associated with playing the computer game on the iPad. Investigators will abide by local IRB 784 reporting requirements.

785 4.6.1 Risk Assessment

786 It is the investigators' opinion that the protocol's level of risk falls under DHHS 46.404 which is 787 research not involving greater than minimal risk.

788 4.7 **Discontinuation of Study**

789 The study may be discontinued by the Steering Committee (with approval of the Data and Safety 790 Monitoring Committee) prior to the preplanned completion of enrollment and follow-up for all 791 subjects.

792 4.8 **Travel Reimbursement**

- 793 Parents of each subject will be compensated \$40 per visit (by check or money-card) for completion
- 794 of each protocol-specified visit, for a maximum of \$160. If there are extenuating circumstances,
- 795 and the subject is unable to complete study visits without additional funds for travel costs,
- 796 additional funds may be provided.

797 4.9 **Study Costs**

- 798 The subject or his/her insurance provider will be responsible for the costs that are considered 799 standard care.
- 800

801 Because the treatment used in the study is not standard of care, the enrollment, 4-, 8, and 16-week

- 802 follow-up visits will be paid for by the study. The cost of the binocular game treatment related
- 803 equipment will also be paid for by the study; however the iPad will need to be returned upon study completion.
- 804
- 805
- 806 Changes in spectacle correction if done (see section 4.3) will be paid for by the study.
- 807

808 **General Considerations** 4.10

- 809 The study is being conducted in compliance with the policies described in the study policies
- 810 document, with the ethical principles that have their origin in the Declaration of Helsinki, with the 811 protocol described herein, and with the standards of Good Clinical Practice.
- 812

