- 352 repeated for the 8-week visit.
- 353

354 **4.4.2 Ocular Alignment**

The proportion of participants with 1) no baseline heterotropia at distance and/or near who developed a new heterotropia (measured by SPCT) at 4 weeks or 2) a baseline heterotropia at distance and/or near (measured by SPCT) who had an increase of $\geq 10\Delta$ in the pre-existing heterotropia at 4 weeks will be reported by treatment group and compared using Barnard's exact test. The analyses will be repeated for

- 359 the 8-week visit.
- 360

361 **4.4.3** Diplopia

The frequency of diplopia was reported as "Never", "Less than once a week", "Once a week", "Once a day", "Up to 10 times a day", "More than 10 times a day", or "All the time". The distribution of diplopia frequency at baseline, 4 weeks, and 8 weeks will be tabulated by treatment group. Each level of diplopia frequency will be assigned an ordered, numeric score. The change in frequency scores (increased by ≥ 2 levels, within 1 level, decreased by ≥ 2 levels) from baseline to 4 and 8 weeks will be tabulated by treatment group. The frequency scores and the change in scores at 4 and 8 weeks will be compared between treatment groups using the exact Wilcoxon rank sum test. The number of participants with

- 369 monocular diplopia (diplopia that does not go away when the eye is closed or covered) will be reported by
- treatment group, but these cases will not be excluded from the analyses.
- 371
- The above analyses will be performed separately for assessments completed by the participant and by theparent.
- 374

375 4.4.4 Adverse Symptoms

Parents were asked to complete a 5-item symptoms survey regarding the frequency of 1) headaches, 2)

- eyestrain, 3) blurry vision, and if wearing spectacles, how often they 4) look over them or 5) take them
- off. The frequency of each survey item was graded as "Never", "Almost never", "Sometimes", "Often",
- or "Almost Always". For each item, the distribution of symptom frequency at baseline, 4 weeks, and 8
- 380 weeks will be tabulated by treatment group. Each level of symptom frequency will be assigned an
- ordered, numerical score. The change in frequency scores (increased by ≥ 2 levels, within 1 level,
- decreased by ≥ 2 levels) from baseline to 4 and 8 weeks will be tabulated by treatment group. The
- frequency scores and the change in scores at 4 and 8 weeks will be compared between treatment groups

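### A strabismus confirmed between visits that resolves before the next scheduled examination, and diplopia that ended more than 2 weeks before a study visit, do not reach the safety analysis, because Protocol 3.10 bars data from the examinations that 4.5.1 calls for

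*Protocol*

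**What the plan says.** Protocol 4.5.1 lists manifest deviation and diplopia among the risks. If treatment precipitates either, "the parent will be advised to have the subject see the investigator as soon as possible". The investigator is expected to confirm a new deviation on examination, and whether therapy continues is left to the investigator and parent.

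Protocol 3.5 schedules examinations at 4 and 8 weeks, plus 16 weeks for spectacle-group children who take up the game. It adds: "Additional non-study visits can be performed at the discretion of the investigator". Protocol 3.10 then states that no data will be "collected at non-study visits for the purpose of the study".

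On adverse events, Protocol 4.6 says "There are no expected long-term adverse events" from playing the game and refers to local IRB reporting. It describes no study event form or log.

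For alignment, SAP 4.4.2 counts participants without baseline heterotropia "who developed a new heterotropia (measured by SPCT) at 4 weeks", or with an increase of at least 10 prism dioptres in an existing one. It repeats this at 8 weeks. Protocol 5.4.3.2 defines the 4-week outcome in similar terms, and SAP 5.4 does so for 16 weeks.

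For diplopia, Protocol 4.5.1 says: "Data on frequency of diplopia will be collected from the child and parent(s) at each study visit". The questionnaire in Protocol 3.8 asks about the presence and "frequency of any diplopia within the last 2 weeks using a standardized diplopia assessment". SAP 4.4.3 analyses those frequencies at 4 and 8 weeks, separately for child and parent report.

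**The concern.** The protocol arranges for the two ocular risks it names to be examined promptly, then excludes the result of that examination from the study data. The exclusion is a stated rule, not a detail left unsaid.

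Events that appear during play and settle before the next visit are the ones exposed to it. In the randomized phase, events precipitated by the game can arise only in the binocular arm, so any loss falls mainly there. Adverse effects were uncommon in the previous trial of a binocular game (Protocol 1.2), and SAP 4.4 tests each safety comparison at a type I error rate of 1%. With few events, a few unrecorded cases could change what readers conclude about alignment and diplopia.

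**Working it through.** The plan states no figure to reproduce. The check is to trace every described route by which an event between visits could reach the analysis, and then to measure what the diplopia look-back covers.

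**Routes into the analysis**

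- *Unscheduled examination (Protocol 4.5.1).* The protocol defines only scheduled study visits and non-study visits, so this falls under 3.10 and yields no study data.
- *Phone call (Protocol 3.4 and 3.5).* It covers compliance and problems with the game. No safety item is described.
- *Adverse event reporting (Protocol 4.6).* Local IRB only.
- *Call to a Protocol Chair (Protocol 4.5.1).* Required if treatment is to be discontinued, but not described as a data record.
- *Treatment deviations (SAP 4.5, item 7).* Defined as crossover or alternative treatment. Stopping play is neither.
- *Strabismus surgery (Protocol 4.4).* Recorded on the Follow-up Examination Form. Section 4.5.1 has no equivalent for a confirmed deviation.
- *Scheduled examination.* Captures alignment on the day, with no look-back.
- *Diplopia questionnaire.* Captures any episode that overlaps the 14 days before the visit.

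**Alignment.** Suppose a tropia is confirmed on day 14 and is absent on day 28. SAP 4.4.2 scores no event at 4 weeks. With no look-back, every episode that clears before the visit is missed. A tropia still present at 4 weeks is counted in the 4-week comparison, even if it has gone by 8 weeks.

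**Diplopia: share of the interval covered.** Formula: 14 / days since the previous visit.

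| Visit timing | Calculation | Covered |
|---|---|---|
| 4-week visit, day 21 (protocol window opens) | 14/21 | 67% |
| 4-week visit, day 28 (nominal) | 14/28 | 50% |
| 4-week visit, day 35 (protocol window closes) | 14/35 | 40% |
| 4-week visit, day 48 (last day of the SAP 3.3 window) | 14/48 | 29% |
| 8-week visit, nominal | 14/28 | 50% |
| 16-week visit, nominal (56 days since week 8) | 14/56 | 25% |

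**Diplopia: share of cleared episodes missed.** Assume one episode of D days, with uniform onset in a 28-day interval, that clears before the visit. Onset can then fall on 28 − D days. The episode is missed if it ends before day 14, so the missed share is (14 − D)/(28 − D) for D up to 14.

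| D (days) | Calculation | Missed |
|---|---|---|
| 1 | 13/27 | 48% |
| 7 | 7/21 | 33% |
| 10 | 4/18 | 22% |
| 14 | 0/14 | 0% |

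The tabulation of maximum diplopia frequency in Protocol 5.4.3.3 does not close this gap, because diplopia data come only from study visits.

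**Weight of one lost case.** With 91 per group in the younger cohort, one child is 1/91 = 1.1 percentage points. With 58 per group in the older cohort, it is 1/58 = 1.7 points. This is a unit of sensitivity, not an estimate of how many are lost.

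**The case against.** Status at a scheduled visit, assessed on the same timetable in both arms, is a legitimate safety measure. The documents never say that they estimate cumulative incidence. On that view nothing is biased, and unscheduled findings are simply outside the measure. This stands as a reason to keep the scheduled comparison as the formal test. It does not explain why an examination that the protocol itself calls for should leave no study record.

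Adding event-driven examinations to the formal test would bring its own bias. They would be more frequent in the binocular arm, whose families know the assignment, and Protocol 3.8 labels acuity and stereoacuity testing as masked but not alignment. SAP 6.0 notes for the older cohort that new deviations were nearly all microtropias, and that their presence can vary with the attention of child and examiner. More looks at a variable sign in one arm would raise its count. This stands, and it is why such findings belong in a descriptive listing.

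The forms, procedures manuals and study policies document are not available here, and treating the prompt examination as a non-study visit is an inference. It is a firm one, since no other visit type is defined, but an event form outside these documents cannot be ruled out.

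A reader might also infer that all diplopia clearing before a visit goes uncounted. The 2-week look-back shows otherwise: an episode is reportable if any part of it fell within those 14 days.

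**Conclusion.** Protocol 3.10 and 4.5.1 need to be reconciled on recording. As written, three things do not reach the safety analysis: new or worsened strabismus confirmed between visits that resolves before the next scheduled examination, diplopia that ended more than 2 weeks before a study visit, and the investigator's confirmation that diplopia was binocular. The same limits apply from week 8 to week 16, with a longer gap between examinations.

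The size of the undercount is unknown. The missed shares for diplopia rest on the assumptions of uniform onset and a single episode, and they apply only to episodes that clear before the visit. The loss would fall mainly on the binocular arm in the randomized phase. A reader might go further and conclude that the alignment comparison is materially biased toward no difference. The documents do not support that, because they report no transient case and no rate.

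**What to change.** 1. **Protocol 3.10.** Add an exception along these lines: *cover test and SPCT findings and binocular diplopia status are recorded on a study form whenever a visit is prompted by a suspected new deviation or diplopia, or treatment is stopped for either.* Refer to it in 4.5.1. This changes recording only, not clinical management.
2. **SAP 4.4.2.** Keep the Barnard comparisons at the scheduled 4- and 8-week visits as the formal tests. Add, by arm, the proportion with a new or worsened heterotropia at either scheduled examination.
3. **SAP 4.4.2 and 4.4.3, and 5.4 for the 8- to 16-week phase.** Report event-driven findings as a descriptive listing and count, by arm in the randomized phase. Note that unscheduled examinations are likely to be more frequent in the binocular arm.

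The cost is one short form for examinations that already take place, one protocol sentence and a few lines in the SAP. Extra detection in the binocular arm is possible, and the descriptive presentation keeps it out of the formal test.

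SAP 4.0 was updated while the younger-cohort manuscript was being drafted, so new data capture may no longer be possible. In that case, add the either-visit count, which needs only data already scheduled, and state the limitation when reporting safety.
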